9. ETHICAL AND REGULATORY CONSIDERATIONS

9.1. Informed Consent

The principles of informed consent, as described in FDA Regulations, will be followed. A subject must give his/her written consent prior to entering the study. This consent will be witnessed and dated and retained by the Investigator as part of the study records. A copy of the consent will be given to the subject.

If the Experimental Subject's Bill of Rights is applicable, this form must also be prepared and signed by each subject and retained as part of the required study records. A copy of the Bill of Rights must be given to the subject. Some states (e.g., California, Oregon, Massachusetts) have additional requirements for the informed consent process; these must be adhered to as well if the clinical site is located in one of these states.

A copy of the proposed consent form must be submitted to the Institutional Review Board (IRB), together with the protocol, for approval. A copy of the IRB-approved consent form must be submitted to the study monitor prior to shipment of drug supplies to the investigator. Each subject's signed informed consent form (ICF) must be kept on file by the investigator for FDA inspection at any time.

9.2. Institutional Review

Any changes to the protocol, as well as a change of investigator, must also be approved by the IRB, and documentation of this approval provided to the study monitor. Records of the IRB review and approval of all documents pertaining to this study must be kept on file by the investigator and are subject to FDA inspection during or after completion of the study. Serious adverse events must also be reported to the IRB. See Section [7.5.5.3](#) for these requirements.

Periodic status reports must be submitted to the IRB at least yearly, as well as notification of completion of the study, and a final report within three months of study completion or termination. A copy of these reports must be sent to Teva Branded Pharmaceutical Products R&D, Inc.

The investigator must maintain an accurate and complete record of all submissions made to the IRB, including a list of all reports and documents submitted. A copy of all site correspondence with the IRB should be sent to the study monitor at Teva Branded Pharmaceutical Products R&D, Inc or designee.

9.3. Drug Accountability

Each shipment of drug supplies to a center will contain an investigational drug invoice to assist the study staff in maintaining current and accurate inventory records covering receipt, dispensing, and the return of study drug supplies. The invoice will identify for each shipment the lot number and the quantity of study drug and supplies contained in the shipment.

When a shipment is received, the investigator or the nurse coordinator must sign the “Shipment Receipt” form verifying the quantities received and retain this form in the study binder. The drug supply will be packaged and shipped to the centers in appropriate containers. If upon arrival at the investigational site the drug supply appears to be damaged, Teva Branded Pharmaceutical Products R&D, Inc. must be contacted immediately and the drug not used until authorized.

Drug supplies must be kept in a secure, limited access storage area under the recommended storage conditions (see Section 5.4). Only authorized personnel will have access to the drug. During the course of the study, the following information must be noted for accurate accountability: the identification code of the subject to whom drug is dispensed, the date(s), and the quantity of drug returned by the subject. Subjects should return all unused pre-filled syringes to the study center and the return noted in the ledger. These will be inventoried for patient compliance and drug accountability. These inventory records must be readily available for inspection by the study monitor and are open to FDA inspection at any time.

When unused pre-filled syringes are to be returned, the investigator or the nurse coordinator will record the returns on the Medication Dispensing CRF verifying the amount of unused pre-filled syringes returned by each study subject. In the event that unused pre-filled syringes are not returned by a subject for whatever reason, this must be explained and whatever attempts to have the syringes returned need to be documented.

Returned study supplies should not remain in the investigator’s possession.

One copy of all inventory record sheets and the return statement will be retained by the investigator for his/her files; the inventory sheets will be included in the return shipment of drug supplies.

Upon completion of the study, all unused pre-filled syringes and the drug accountability information must be returned to the sponsor, Teva Branded Pharmaceutical Products R&D, Inc. or sponsor’s designee. Teva Branded Pharmaceutical Products R&D, Inc. or designee will handle the destruction of unused syringes.

9.4. Clinical Product Complaints

A clinical product complaint is defined as a problem or potential problem with the physical quality or characteristics of clinical drug supplies or clinical device supplies used in a clinical research study sponsored by Teva. Examples of a product complaint include but are not limited to:

- suspected contamination
- questionable stability (eg, color change, flaking, crumbling, etc)
- defective components
- missing or extra units (eg, primary container is received at the investigational center with more or less than the designated number of units inside)

- incorrect packaging, or incorrect or missing labeling/labels
- unexpected or unanticipated taste or odor, or both
- device not working correctly or appears defective in some manner

Each investigational center will be responsible for reporting a possible clinical product complaint by completing the product complaint form provided by Teva and emailing it to [REDACTED] within 48 hours of becoming aware of the issue.

For complaints involving a device or other retrievable item, it is required that the device (or item) be sent back to the sponsor for investigative testing whenever possible. For complaints involving a drug product, all relevant samples (eg, the remainder of the patient's drug supply) should be sent back to the sponsor for investigative testing whenever possible.

9.4.1. Product Complaint Information Needed from the Investigational Center

In the event that the product complaint form cannot be completed, the investigator will obtain the following information, as available:

- investigational center number and principal investigator name
- name, phone number, and address of the source of the complaint
- clinical protocol number
- patient identifier (patient study number) and corresponding visit numbers, if applicable
- product name and strength for open-label studies
- patient number, bottle, and kit numbers (if applicable) for double-blind or open-label studies
- product available for return Yes/No
- product was taken or used according to protocol Yes/No
- description or nature of complaint
- associated serious adverse event Yes/No
- clinical supplies unblinded (for blinded studies) Yes/No
- date and name of person receiving the complaint

Note: Reporting a product complaint must not be delayed even if not all the required information can be obtained immediately. Known information must be reported immediately. The sponsor will collaborate with the investigator to obtain any outstanding information.

9.4.2. Handling of Study Drug at the Investigational Center

The investigator is responsible for retaining the product in question in a location separate from the investigator's clinical study supplies. The sponsor may request that the investigator return the product for further evaluation and/or analysis. If this is necessary, the clinical study monitor or designee will provide the information needed for returning the study drug.

If it is determined that the investigational center must return all study drug, the sponsor will provide the information needed to handle the return.

The integrity of the randomization code and corresponding blinded clinical supplies will be maintained whenever possible. A serious adverse event or the potential for a product quality problem existing beyond the scope of the complaint may be a reason to unblind the clinical supplies for an affected patient.

9.4.3. Adverse Events or Serious Adverse Events Associated with a Product Complaint

If there is an adverse event or serious adverse event due to product complaint, the protocol should be followed for recording and reporting (Section [7.5.5.3](#)).

9.4.4. Documenting a Product Complaint

The investigator will record in the source documentation a description of the product complaint, and any actions taken to resolve the complaint and to preserve the safety of the patient. Once the complaint has been investigated by the sponsor and the investigator, if necessary, an event closure letter may be sent to the investigational center where the complaint originated or to all investigational centers using the product.

9.5. Case Report Forms

Case Report Forms (CRF) for individual subjects will be provided by Teva Branded Pharmaceutical Products R&D, Inc. Each CRF page will be a three-part no carbon required (NCR) form, with copies for the study site and Teva Branded Pharmaceutical Products R&D, Inc. CRFs are used to record study data and are an integral part of the study and subsequent reports. Therefore, the CRFs must be legible and complete. All forms should be filled out using a black ball point pen. Errors should be lined out, but not obliterated, and the correction inserted, initialed, and dated by the person making the correction. A CRF must be completed and signed by the investigator or subinvestigator listed on the FDA Form 1572, for each subject enrolled, including those subjects terminated from the study for any reason. The reason for termination must be noted on the Termination Visit CRF.

CRFs must be kept current to reflect subject status at each phase during the course of the study. Subjects are not to be identified on CRFs by name; appropriate coded identification and subject

initials must be used. The study staff must keep a separate log of subject names and addresses. This log is not subject to FDA inspection.

Because of the potential for errors, inaccuracies, and illegibility in transcribing data onto CRFs, originals of laboratory and other test results must be kept on file with the subject's CRF or clinic chart. CRFs and copies of test results must be available at all times for inspection by the study monitors and FDA.

Data collected from visit month 159 through the completion of the study will be recorded on electronic CRFs (eCRF). Paper CRFs may continue to be used in conjunction with the eCRFs, but will not be collected upon completion.

9.6. Study Administration

9.6.1. Continuation of Study

Prior to the continuation of the study, the following items must be received from the investigator:

- Letter of IRB approval.
- A signed copy of the protocol.
- A copy of the ICF approved by the IRB.
- The investigator's current curriculum vitae as well as the curriculum vitae of any subinvestigator(s).

9.6.2. Monitoring the Study

Regular monitoring of the study data at each site will be performed in accordance with FDA regulations (see 21 CFR 312 e.t. seq). Individual sites will be monitored periodically at the discretion of the sponsor to ascertain that data recording and protocol adherence are satisfactory. Additional monitoring will be performed by telephone, mail, or site visit as needed.

9.6.3. Interpretation of the Protocol

The procedures defined in the protocol and in the Case Report Forms will be carefully reviewed at the time of the extension to ensure standardized interpretation and implementation. In order to ensure validity of the data, with minimal exceptions, no deviations from the protocol may be made unless the issue is broad enough to warrant revisions of the protocol for all sites. Such changes must be approved by the study sponsor and communicated in writing to the FDA by the sponsor.

Such revisions must be submitted to and have approval in writing from the appropriate Institutional Review Board (IRB) prior to implementation.

9.6.4. Maintenance of Study Documentation and Supplies

It is the responsibility of the investigator and the study staff to maintain a comprehensive and centralized filing system of all relevant study documentation. A Regulatory Binder will be provided by Teva Branded Pharmaceutical Products R&D, Inc. for maintaining such documentation in a central location. Such documentation includes:

- Case Report Forms: Must be kept legible, accurate, and up-to-date.
- Patient Files: These substantiate the data entered in the CRFs with regard to lab data, patient histories, treatment regimens, etc.
- Patient Exclusion Record: Should reflect the reason any patient was screened for this study and excluded.
- Drug Dispensing Log: Should reflect the total amount of pre-filled syringes received and returned to the sponsor, and the amount distributed and returned by each patient. This information must agree with the information entered in the CRFs.
- ICFs: Must be available for each patient and be verified for proper documentation.
- Comments Page: This section of the CRF is to be utilized to explain any aspect of the study that is not easily entered on the routine CRFs, and would include such items as:
 - Protocol deviation(s).
 - Comments or explanations of unusual findings.
 - Any data or clarification of data not explicitly requested on the CRFs.
 - Description of details and duration of relapse(s).

Federal regulations require that all items listed under Initiation of Study (Section 9.6.1), Maintenance of Study Documentation and Supplies (Section 9.6.4), protocol amendments and their IRB approvals, revised FDA Form 1572 forms, correspondence, and any other documents pertaining to the conduct of the study, must be kept on file by the investigator until notified by the sponsor.

9.7. Patient Confidentiality

All participants are concerned for the individual patient's privacy and, therefore, all patient data will be identified only by a patient identification number and patient initials. However, in compliance with federal guidelines regarding the monitoring of clinical studies and in fulfillment of his/her obligations to the sponsor, it is required that the investigator permit the study monitor and/or FDA representative to review that portion of the patient's medical record that is directly related to the study. This shall include all study-relevant documentation including patient medical histories to verify eligibility, laboratory test result reports to verify transcription

accuracy, admission/discharge summaries for hospital admissions occurring while the patient is enrolled in the study and autopsy reports for deaths occurring during the study.

As part of the required content of informed consent, the patient must be informed that his/her medical chart may be reviewed by the sponsor, the sponsor's authorized representative, or a representative of the FDA. Should access to the medical record require a separate waiver or authorization, it is the investigator's responsibility to obtain such permission from the patient in writing before the patient is entered into the study.

10.2. Project Director

The Project Director will be responsible for the clinical aspects of the trial. This individual will also interact frequently with the study sponsors and be consulted for clinical interpretations regarding the study.

10.3. Principal Investigator

The Principal Investigator will be responsible for the clinical aspects of the trial at his/her site. He/she will assist with patient recruitment to the trial and will assure compliance with the clinical trial protocol.

10.4. Project Manager

The Project Manager will be responsible for the organizational aspects and day-to-day activities of the trial.

10.5. Medical Monitor

The Medical Monitor will review Serious Adverse Events.

10.6. Study Coordinator

Each site will appoint a study coordinator who will assist the investigator and his/her associates. The study coordinator will be responsible for patient scheduling and for completing and maintaining the Case Report Forms and all other patient records, including the consent form, in an orderly and confidential manner. The study coordinator will record local and systemic side effects. The study coordinator will also be responsible for collecting and forwarding clinical samples and requests to appropriate laboratories and obtaining and forwarding laboratory results.

10.7. Project CRA / Study Monitor

The study monitor/CRA for this trial will be provided by Teva Branded Pharmaceutical Products R&D, Inc. The study conduct will be monitored in accordance with GCP/ICH guidelines, applicable SOPs, and as per protocol.

APPENDIX A. SCHEDULE OF ACTIVITIES AND EVALUATIONS

Procedures Performed	Study Visit				
	Screening Visit for Amendment 13 (Month 264) ^a	Unscheduled Visits as necessary for Protocol	Nurse Coordinator Telephone Visits ^b	Investigator Visits (Month 276)	Termination Visit (scheduled Month 288)
Study Extension Informed Consent	X				
Visit Checklist	X	X	X	X	X
Evidence of Relapse	X	X ^c	X	X	X
Physical Examination	X	X ^c			X
Urinalysis	X	X ^c		X	X
Hematology	X	X ^c		X	X
Serum Chemistries	X ^d	X ^{c,d}		X	X
Serum/Pregnancy Test (where appropriate)		X ^c			X ^e
Adverse Experiences	X	X ^c	X	X	X
Concomitant Therapy	X	X ^c	X	X	X
Medication History		X ^c			
Record Treatment	X			X	
Drug Accountability	X	X ^c	X	X	X
Neurological Assessments	X	X ^c		X	X
Termination Reason					X ^e
Optional MRI	X	X ^c			

^a This will be the same visit as the termination visit for Amendment 12, except for patients who completed the termination visit of Amendment 12 but were not able to immediately enter Amendment 13; for these patients, the Amendment 13 visit will be distinct from the Amendment 12 termination visit.

^b Months 267, 270, 273, 279, 282, and 285

^c Optional as deemed necessary for the visit

^d Serum creatinine should be obtained prior to an MRI scan

^e For early termination only.

APPENDIX B. DEFINITION OF RELAPSE

The following: "relapse," "exacerbation," "attack," and "bout" are equivalent terms. The term "relapse" will be used throughout this protocol. A relapse is defined as the appearance of one or more new neurologic abnormalities or the reappearance of one or more previously observed neurologic abnormalities. This change in clinical state must last at least 48 hours and be immediately preceded by a relatively stable or improving neurologic state in the 30 days before deterioration. An event is counted as a relapse only when the patient's symptoms are accompanied by observed objective changes on the neurologic examination consistent with an increase of at least 0.5 on the EDSS ([Appendix C](#)) or one grade in the score for two or more of the seven functional systems (FS) ([Appendix D](#)) of Kurtzke or two grades in the score for one of the FS as compared to the previous evaluation. The patient must not be undergoing an acute metabolic change such as fever or other medical abnormality, and a change in bowel/bladder or in cognitive function must not be entirely responsible for the changes in EDSS or FS scores.

APPENDIX C. KURTZKE EXPANDED DISABILITY STATUS SCALE (EDSS) IN MULTIPLE SCLEROSIS

Note: EDSS steps below 5 refer to patients who are fully ambulatory and the precise step is defined by the Functional System (FS) score(s). EDSS steps from 5 up are defined by ability to ambulate, and usual equivalents in FS scores are provided. A mental function grade of 1 does not enter into FS scores for EDSS steps. EDSS should not change by 1.0 step unless there is a change in same direction of at least one step in at least one FS

- 0 = Normal neurologic exam (all grade 0 in Functional Systems (FS); Cerebral grade 1 acceptable).
- 1.0 = No disability, minimal signs in one FS (i.e., grade 1 excluding Cerebral grade 1).
- 1.5 = No disability, minimal signs in more than one FS (more than one grade 1 excluding Cerebral grade 1).
- 2.0 = Minimal disability in one FS (one FS grade 2, others 0 or 1).
- 2.5 = Minimal disability in two FS (two FS grade 2, others 0 or 1).
- 3.0 = Moderate disability in one FS (one FS grade 3, others 0 or 1), or mild disability in three of four FS (three/four FS grade 2, others 0 or 1) though fully ambulatory.
- 3.5 = Fully ambulatory but with moderate disability in one FS (one grade 3) and one or two FS grade 2; or two FS grade 3; or five FS grade 4 (others 0 or 1).
- 4.0 = Fully ambulatory without aid, self-sufficient, up and about some 12 hours a day despite relatively severe disability consisting of one FS grade 4 (others 0 or 1), or combinations of lesser grades exceeding limits of previous steps.
- 4.5 = Fully ambulatory without aid, up and about much of the day, able to work a full day, may otherwise have some limitation of full activity or require minimal assistance; characterized by relatively severe disability, usually consisting of one FS grade 4 (others 0 or 1) or combinations of lesser grades exceeding limits of previous steps. Able to walk without aid or rest some 300 meters.
- 5.0 = Ambulatory without aid or rest for about 200 meters; disability severe enough to impair full daily activities (e.g., unable to work full day without special provisions). (Usual FS equivalents are one grade 5 alone, others 0 or 1; or combinations of lesser grades usually exceeding specifications for step 4.0.)

- 5.5 = Ambulatory without aid or rest for about 100 meters; disability severe enough to preclude full daily activities. (Usual FS equivalents are one grade 5 alone, others 0 or 1; or combinations of lesser grades usually exceeding those of step 4.0.)
- 6.0 = Intermittent or unilateral constant assistance (cane, crutch, or brace) required to walk about 100 meters without resting. (Usual FS equivalents are combinations with more than two FS grade 3+.)
- 6.5 = Constant bilateral assistance (canes, crutches, or braces) required to walk about 20 meters without resting. (Usual FS equivalents are combinations with more than FS grade 3+.)
- 7.0 = Unable to walk beyond about 5 meters even with aid, essentially restricted to wheelchair; wheels self in standard wheelchair and transfers alone; up and about in wheelchair some 12 hours a day. (Usual FS equivalents are combinations with more than one FS grade 4+; very rarely, pyramidal grade 5 alone.)
- 7.5 = Unable to take more than a few steps; restricted to wheelchair; may need aid in transfer; wheels self but cannot carry on in standard wheelchair a full day; may require motorized wheelchair. (Usual FS equivalents are combinations with more than one FS grade 4+.)
- 8.0 = Essentially restricted to bed or chair or perambulated in wheelchair, but may be out of bed itself much of the day; retains many self-care functions; generally has effective use of arms. (Usual FS equivalents are combinations, generally grade 4+ in several systems.)
- 8.5 = Essentially restricted to bed much of the day; has some effective use of arm(s); retains some self-care functions. (Usual FS equivalents are combinations, generally 4+ in several systems.)
- 9.0 = Helpless bed patient; can communicate and eat. (Usual FS equivalents are combinations, mostly grade 4+.)
- 9.5 = Totally helpless bed patient; unable to communicate effectively or eat/swallow. (Usual FS equivalents are combinations, almost all grade 4+.)
- 10.0 = Death due to MS.

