APPENDIX D. FUNCTIONAL SYSTEM SCALE STUDIES (FS)

Pyramidal Functions:

0 = Normal

1 = Abnormal signs without disability

2 = Minimal Disability

3 = Mild or moderate paraparesis, hemiparesis or severe monoparesis

4 = Marked paraparesis or hemiparesis or moderate quadriparesis or monoplegia

5 = Paraplegia, hemiplegia, or marked quadriparesis

6 = Quadriplegia

Cerebellar Functions:

0 = Normal

1 = Abnormal signs without disability

2 = Mild ataxia

3 = Moderate limb or truncal ataxia

4 = Severe ataxis in all limbs

5 = Unable to perform coordinated movements

Brain Stem Functions:

0 = Normal

1 = Signs only

2 = Moderate nystagmus or other mild disability

3 = Severe nystagmus, marked extraocular weakness or moderate disability of other cranial nerves

4 = Marked dysarthria or other marked disability

5 = Inability to swallow or speak

Mental Functions:

- 0 = Normal
- 1 = Mood alteration only
- 2 = Mild decrease in mentation
- 3 = Moderate decrease in mentation
- 4 = Marked decrease in mentation
- 5 = Dementia and/or chronic depressed alertness

Other Functions:

- 0 = Normal
 - 1 = Any other findings (specify below):
-

Sensory Functions:

- 0 = Normal
- 1 = Vibration or figure writing decrease in 1 or 2 limbs
- 2 = Mild decrease in touch or pain or position sense and/or moderate decrease in vibration in 1 or 2 limbs; or vibratory decrease alone in 3 or 4 limbs
- 3 = Moderate decrease in touch or pain or position sense and/or essentially lost vibration in 1 or 2 limbs; or mild decrease in touch or pain and/or moderate decrease in all proprioceptive tests in 3 or 4 limbs
- 4 = Marked decrease in touch or pain or proprioception alone or combined in 1 or 2 limbs; or moderate decrease in touch or pain and/or severe proprioceptive loss in more than 2 limbs
- 5 = Loss of sensation in 1 or 2 limbs; or moderate decrease in touch or pain and/or loss of proprioception below the head
- 6 = Sensation lost below the head

Bowel & Bladder Functions:

0 = Normal

1 = Mild urinary hesitancy, urgency, or retention

2 = Moderate hesitancy, urgency, retention of bowel or bladder or rare urinary incontinence

3 = Frequent urinary incontinence

4 = In need of almost constant catheterization but with adequate bowel function

5 = Loss of bladder function

6 = Loss of bowel and bladder function

Visual Functions:

0 = Normal

1 = Acuity better than 20/30 in the worse eye

2 = Acuity between 20/30 and 20/59 in worse eye

3 = Acuity between 20/60 and 20/99 in worse eye

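### As printed, EDSS step 3.5 (Appendix C) and visual grade 4 (Appendix D) conflict with the entries beside them, leaving a small set of scores and borderline relapse calls unsettled.

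*Combined protocol and SAP*

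**What the plan says.** Appendix C states that "EDSS steps below 5 refer to patients who are fully ambulatory and the precise step is defined by the Functional System (FS) score(s", whereas "EDSS steps from 5 up are defined by ability to ambulate". The entries that matter are these:

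- Step 3.0 includes "mild disability in three of four FS (three/four FS grade 2, others 0 or 1").
- Step 3.5 closes with "or two FS grade 3; or five FS grade 4 (others 0 or 1").
- Step 4.0 is "one FS grade 4 (others 0 or 1), or combinations of lesser grades exceeding limits of previous steps".
- Step 4.5 is a level "usually consisting of one FS grade 4 (others 0 or 1) or combinations of lesser grades exceeding limits of previous steps".

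In Appendix D (Visual Functions), grade 2 covers worse-eye acuity from 20/30 to 20/59. Grade 3 is "Acuity between 20/60 and 20/99 in worse eye". Grade 4 is given as 10/100 to 20/200 in the worse eye, or grade 3 with a better eye of 20/60 or less. Grade 5 begins at 20/200 or less in the worse eye.

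Appendix B counts a relapse only if the examination shows a change consistent with one of three limbs: a rise of at least 0.5 EDSS, one grade in two or more FS, or two grades in one FS. It refers to Appendices C and D for the scores. Section 7.1.4 sends the neurologist to these appendices when a relapse is suspected. Section 3 lists FS, EDSS and exacerbations among the objectives.

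**The concern.** Both entries look like faults in the scoring key itself. Five systems at grade 4 cannot sensibly rank below one system at grade 4. A visual range whose two ends are the same acuity is not a range. Below EDSS 5 the FS grades set the step, and relapse is judged by small differences in these scores. A faulty key can therefore change the recorded disability change or decide whether a relapse limb is met. With about 60 patients and descriptive reporting, a single reclassified relapse would be visible.

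**Working it through.** The plan gives no figure to reproduce, so the check sets the entries side by side and counts the patterns affected.

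**Inputs.** The EDSS steps and the note come from Appendix C, the visual grades from Appendix D, and the relapse limbs from Appendix B, which also says that bowel/bladder or cognitive change must not be entirely responsible. One assumption is added: the comparison key puts five FS at grade 2 at step 3.5. This is inferred from the adjacent steps and is not stated in the documents.

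**1. EDSS steps, read in order**

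| FS pattern (others 0 or 1) | As printed | If five at grade 2 = 3.5 |
|---|---|---|
| Four at grade 2 | 3.0 | 3.0 |
| Five at grade 2 | 4.0 (residual clause) | 3.5 |
| Four at grade 2, one at grade 3 | 4.0 (residual clause) | 4.0 |
| Six at grade 2 | 4.0 (residual clause) | 4.0 |
| One at grade 4 | 4.0 | 4.0 |
| Five at grade 4 | 3.5 | not listed at 3.5 |

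**2. Effect on the 0.5 EDSS limb**

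- Four to five systems at grade 2: 4.0 − 3.0 = +1.0 as printed, 3.5 − 3.0 = +0.5 under the comparison key. The limb is met either way; only the recorded size differs.
- Five at grade 2, then one more one-grade worsening in a single FS (2 to 3, or 1 to 2): 4.0 − 4.0 = 0 as printed, 4.0 − 3.5 = +0.5 under the comparison key. The other two limbs are not met by one grade in one system, so here the EDSS limb depends on the key.

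**3. How many patterns** (seven FS, grades 0 to 3, mental grade 1 not counted, residual patterns held at 4.0)

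- All patterns: 4^7 = 16,384. Exactly five at grade 2, others 0 or 1: C(7,5) × 2² = 21 × 4 = 84. Share: 84 / 16,384 = 0.51%.
- One-grade worsenings in one of the five systems other than bowel/bladder and mental: 5 × 3 × 4^6 = 61,440.
- Change of +1.0 versus +0.5 (four to five at grade 2): 5 × C(6,4) × 2² = 300, or 0.49%. The limb is unaffected.
- Change of 0 versus +0.5: grade 2 to 3 gives 5 × C(6,4) × 2² = 300, and grade 1 to 2 gives 5 × C(6,5) × 2 = 60. Total 360, or 360 / 61,440 = 0.59%.
- If a rater uses the functional text to score those 360 as 4.0 to 4.5, the limb is met as printed and none differ. The range is 0 to 360 (0 to 0.59%).

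**4. Visual grade 4 range**

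- 10/100 = 0.10 and 20/200 = 0.10, so the printed range is one point.
- Grade 3 stops at 20/99 and grade 5 starts at 20/200, so 20/100 to 20/199 has no printed worse-eye grade. The better-eye clause of grade 4 does not help, because it requires grade 3 first.
- Example: 20/50 to 20/120 goes from grade 2 to no printed grade. If the rater infers grade 4, the change is 4 − 2 = 2 grades and the single-FS limb is met. If the rater stays at grade 3, it is 1 grade and the limb is not met.

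**5. The shared boundary at 20/200** (a separate matter)

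- 20/200 fits grade 4 and grade 5. A fall from 20/70 (grade 3) to 20/200 is therefore +1 (limb not met) or +2 (limb met).
- Reading 10/100 as 20/100 closes the gap in step 4 but leaves this overlap.

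The visual examples isolate the single-FS limb when EDSS is 5 or more, because ambulation then sets the step. Below 5, a visual change may also move EDSS and meet the 0.5 limb by that route.

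**The case against.** The strongest case on the other side is that these are small slips in a reproduced standard scale, used by neurologists who know it, with no shown consequence. Much of it stands.

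- **The text may be misread.** Each main conflict turns on one digit or pair of digits in text taken from a PDF. An extraction error cannot be excluded, so the page check must come first.
- **The key still gives an answer for five systems at grade 2.** A reader might infer that raters may choose freely between 4.0 and 4.5, because the two steps share their FS wording. The documents do not support that. The steps differ in functional text (hours up and about, full working day, minimal assistance, 300 metres), and a literal reader working in order arrives at 4.0. The answer is probably unintended, but it is not arbitrary.
- **Relapse is not a table lookup.** Appendix B also requires 48 hours' duration, 30 days of prior stability and no fever or other acute medical abnormality, and Section 7.1.4 leaves the decision to follow the neurologist's examination.
- **No planned result is shown to move.** Section 8 promises standard reporting of the neurologic course but details only adverse events and laboratory tests.

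What does not stand is the suggestion that this is background text. Sections 7.1.1 and 7.1.4 and Appendix B direct raters to these keys, and the supplied documents name no other scoring manual.

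**Conclusion.** Wrong as written, and minor. The step 3.5 entry and the visual grade 4 range contradict their neighbours as printed. The consequence is confined to patterns with five systems at grade 2 or at grade 4, worse-eye acuity from 20/100 to 20/199, and the shared point at 20/200. The counted EDSS effect, covering grades 0 to 3, is 84 of 16,384 patterns and 0 to 360 of 61,440 one-grade worsenings. It rests on the assumption that five systems at grade 2 belong at 3.5 and on equal weight for every pattern. How many of the roughly 60 patients it touches is unknown. No percentage is offered for the visual entry.

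A reader might go further and infer that EDSS scores or relapse counts in this study are wrong, or that the relapse thresholds are faulty. The documents support neither: no mis-scored visit is shown, nothing establishes that raters scored from this text, and the thresholds in Appendix B are not themselves in error. Nor should the 20/200 ambiguity be put down to the 10/100 entry; it arises because grades 4 and 5 both name that acuity.

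**What to change.** 1. Check the original page and the source scales for both entries.
2. If the errors are confirmed, correct step 3.5 to agree with steps 3.0 and 4.0, correct visual grade 4 so that it begins where grade 3 ends, and reconcile the shared 20/200 boundary of grades 4 and 5 with the source scale.
3. On the same pass, look at the wording of step 3.0 (three of four, against three or four) and at step 6.5, where "combinations with more than FS grade 3" appears to lack a count.
4. State which version of the scales the raters used. The review of procedures promised in Section 9.6.3 is the natural place.
5. Only if the raters used the printed text, run one listing of visits whose recorded EDSS below 5 conflicts with the FS grades, and flag any relapse decision that would change. Visual grades can be queried only where source records hold worse-eye acuity, since no visit checklist names it.

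The cost is a page check and a few corrected words. The listing, if needed, is a single query, with the small downside that some historical scores are reopened.
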